recurrent cancer 2-months ahead of schedule. At the time of enrollment, 27 patients had recurrent cancer. Enrollment rates were 78% and similar among patients with new versus recurrent cancer. Thirteen experienced progressive disease during the study observation period, and 18 died of disease or treatment-related mortality prior to the 6-month end-point, including 5 of the 27 who enrolled with recurrent cancer. Attrition among surviving participants was similar on the PRISM (25%) and usual care (14%) arms, and primarily due to medical complications. Of 49 AYAs assigned to PRISM, 48 completed  $\geq 1$ , and 43 completed all scheduled sessions. Only 2 PRISM and 6 usual care patients declined continued participation due to the burden of intervention sessions or surveys.

The primary objective of the phase II RCT was to assess patient-reported resilience 6 months following enrollment. Secondary outcomes included psychological distress and HRQOL at the same time-point. Final pilot results ( $n=92$  with intention-to-treat analyses) suggest the intervention was associated with improved patient-reported resilience, distress, and quality of life scores with moderate effect sizes (**Table 2**). Exploratory analyses suggested a stronger intervention effect among AYAs who enrolled with advanced cancer (**Figure 2**). Taken together, these findings are promising because: (a) meta-analyses suggest even small effect sizes of positive psychology interventions are associated with clinically meaningful patient-centered outcomes; (b) we demonstrated feasibility among the sickest patients with advanced cancer; and, (c) the intervention may be even more impactful in this high risk group of patients.

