## 9.5 Data collection schedule for study staff.

### 9.5.1 For the AYA and caregiver survey schedules for both the run in and RCT, please see

Figures 3A and 3B. Medical record data will be collected at baseline and monthly until the 3-month mark in both the run in and RCT. Additional medical record abstraction will occur for the RCT at 6-, 9, and 12-months. The caregiver to complete the surveys will be designated at enrollment. RA's at each site will prospectively abstract information from the medical record using a study-specific case report form (CRF) adapted from prior studies. This will include: (1) AYA participation in goals of care conversations: dates of documented conversations with medical team regarding prognosis, treatment decisions, and/or goals of care, whether or not AYA was present, and if there is documented active AYA participation. (2) Benchmarks of Palliative Care Utilization: number and frequency of documented psychosocial and palliative care referrals and meetings, hospice referrals, limitation-of-resuscitation orders, completion of advance care planning documents, and end of life details (i.e. location of death, clinical involvement and family support (sibling & financial assessments)). (3) Clinical covariates: the AYA's diagnosis, cancer/tumor-directed treatments, and intensity in the past month, number of and reason for hospital days

(anticipated and unanticipated), prescription psychiatric and/or mood altering medications, prescription opioids and other pain medications, and number of documented palliative care/psychosocial encounters. These variables were selected based on prior evidence that child well-being and family psychosocial needs affect immediate psychosocial outcome metrics (e.g., psychological distress and quality of life).

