### 11.5.3 Secondary Outcomes

**11.5.3.1** The goal for parent outcomes is to evaluate the effect of the intervention on *parent psychological distress* and HRQOL. Mean total scores from each parent instrument at 12 weeks will be the secondary outcomes of interest. We will model distress and HRQOL separately and follow a similar approach to the analyses for continuous outcome measures in Aim 1. As sex and baseline patient HRQOL may be predictors of these outcomes, each will be included if imbalanced between arms.

**11.5.3.2** To compare patient and caregiver *activation*, we will measure patterns in multiple domains: AYA- and parent-reported Decision-Making Involvement Scores, AYA participation in goals of care conversations, and formal palliative care service utilization including documented referrals for hospice and charted decisions to limit resuscitative efforts. For all outcomes, results between trial groups will be compared using analysis of variance with trial group as the factor of interest. We will explore whether change in activation scores are correlated within families and/or modified by parent/child characteristics (sex, psychological distress scores, cancer/tumor-type, among others) using ordinal logistic regression models with cumulative logits, where change activation level is categorized as negative, null, or positive.

**11.5.3.3 Exploratory analyses** will evaluate prospective and longitudinal survey and clinical data beyond month 3 (primary endpoint) at months 6, 9, and 12 of the study. Comparisons between groups will still use an intention to treat approach as described above. Additionally, we will explore the relationship between biomedical variables and patient reported anxiety and depression through a combination of paired and unpaired t-tests, chi-squared (or Fisher's exact) tests, and linear and logistics regression. HRV will be measured in 24-hour increments using both time and frequency domain parameters as established by the international Cardiology task force

guidelines. Means and standard deviations will be compared to published normative data in adolescents.

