
#### **14.2 Early Withdrawal of Subjects**

All participants may choose to withdraw from the study at any time. We will track date of discontinuation and request a brief reason to be recorded for tracking purposes. In the event of serious medical complications (or death) precluding participation, participants will be censored after 2 months of missing data. In all other cases, staff will continue to request surveys until 2 months following the study endpoint (12 months for RCT, 3 months for Run-In), as described above.

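### Activation chart outcomes that are counts or yes/no events are assigned to ANOVA with no rule for shortened chart time; name count and binary models and a death and follow-up rule

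*Combined protocol and SAP*

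**What the plan says.** Section 1.2.3.5 makes family activation a secondary aim with its own directional hypothesis (1.2.3.5.2). Section 11.5.3.2 lists the outcomes: Decision-Making Involvement scores from AYAs and parents, AYA participation in goals-of-care conversations, and "formal palliative care service utilization including documented referrals for hospice and charted decisions to limit resuscitative efforts". It then sets one method: "For all outcomes, results between trial groups will be compared using analysis of variance with trial group as the factor of interest". The ordinal logistic model that follows only explores within-family correlation and effect modification of change scores.

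Section 9.5.1 shows what kind of data these are. Site staff abstract the dates of documented conversations and whether the AYA was present and took part. They also abstract "number and frequency of documented psychosocial and palliative care referrals and meetings, hospice referrals, limitation-of-resuscitation orders, completion of advance care planning documents". The schedule is fixed: "Medical record data will be collected at baseline and monthly until the 3-month mark in both the run in and RCT", and "Additional medical record abstraction will occur for the RCT at 6-, 9, and 12-months".

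Three other sections bear on the point:
- 11.5.1 adjusts all analyses for site and age. 11.5.2 extends the baseline-adjusted regression to secondary outcomes in the AYA survey.
- 11.5.3.6 names record omissions, lack of follow-up, medical complications and death as causes of missing data. It offers multiple imputation or inverse probability weighting under MAR, and sensitivity analyses under MNAR.
- 14.2 says that after death or serious complications that preclude participation "participants will be censored after 2 months of missing data".

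**The concern.** A raw total or a yes/no indicator by month 3 depends on how long the chart was open to observation. In this population some AYAs will die, move to another centre or be lost before month 3, so observation time will vary between people. Section 11.5.3.2 does not say whether a shortened window is scored as it stands, scaled to time observed, imputed or excluded. Hospice referral and limits on resuscitation are closely tied to approaching death, so the choice matters more for them than for a survey score.

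A second gap concerns AYA participation, which is recorded per documented conversation. PRISM-AC is meant to prompt such conversations (section 9.4). A comparison made only among AYAs who had one would condition on something that the intervention may change. The plan does not say that it will do this, but it does not say how an AYA with no conversation is scored.

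At stake is the interpretation of the chart part of the activation hypothesis. If the count model, binary model and death rule are chosen after the data are seen, that result is open to selective analysis.

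**Working it through.** **The plan's own figure.** The documents give no event rate, effect size or power for any activation outcome. The only sample-size target is the primary one, and it reproduces. The number needed per arm is 2 × (1.96 + 0.842)² × 17.2² / 8.1² ≈ 71, against 72 stated, and power at 72 per arm is 80.1% (t-based). Then 144 / (1 − 0.26) ≈ 195.

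**Inputs.** From the documents: 98 randomized per arm, 5% type I error (taken as two-sided), 1:1 allocation. Assumed, because the documents give nothing: a control mean of 1.5 events at full follow-up, a rate ratio of 1.5 (so 2.25 on PRISM), negative binomial dispersion k of 0.5 or 1, and exponentially distributed end of chart follow-up.

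**1. Yes/no events, full follow-up.** By exact enumeration at 72 and 98 per arm, ANOVA has type I error of 4.2% to 5.2% for event rates of 3% to 40%. For 20% against 40% at 72 per arm, power is 75.4% with ANOVA and 75.7% with chi-square.

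**2. Counts, full follow-up.** The variance of a count with mean μ is μ + kμ². With k = 1:
- ANOVA: difference 2.25 − 1.5 = 0.75; SE = √[(3.75 + 7.3125)/98] = 0.336; z = 2.23; power Φ(2.23 − 1.96) ≈ 61%.
- Rate model: SE of the log ratio = √[(1/1.5 + 1/2.25 + 2)/98] = 0.178; z = 0.405/0.178 = 2.28; power ≈ 62%.

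With k = 0.5 the same formulas give 78% and 79%. Simulation gave 59–79% for ANOVA and 60–80% for the rate model.

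**3. Mean chart time.** If a fraction d is lost by the end of the window, mean observed time as a share of the window is d / [−ln(1 − d)].
- d = 14%: 0.14/0.1508 = 0.928
- d = 25%: 0.25/0.2877 = 0.869
- Ratio: 0.869/0.928 = 0.936

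With 14% lost on usual care and 25% on PRISM, PRISM has about 6% less chart time.

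**4. Counts, unequal follow-up.** Expected raw means are 1.5 × 0.928 = 1.39 and 2.25 × 0.869 = 1.96, a ratio of about 1.40. The simulated mean ratio was 1.42 to 1.43. It is slightly higher because an average of ratios runs high: the same simulation gave 1.52 to 1.53 under equal loss, where the truth is 1.5. With no true effect the raw ratio comes out between 0.93 and 0.96, depending on whether the median or the mean of the simulated ratios is reported, and type I error is about 6% to 7.5%.

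**5. Power for counts at a true rate ratio of 1.5 (simulated).**

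| Chart follow-up lost | k | ANOVA on raw counts | Rate model with offset |
|---|---|---|---|
| 19% in both arms | 0.5 | 73.7% | 77.5% |
| 19% in both arms | 1 | 55.7% | 59.4% |
| 14% usual care, 25% PRISM | 0.5 | 57.9% | 76.9% |
| 14% usual care, 25% PRISM | 1 | 39.3% | 57.9% |

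Equal loss costs about 4 points and unequal loss about 19. A separate simulation of the unequal case with k = 1 gave 44.9% against 60.2%, a gap of 15 points.

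**6. Yes/no events, unequal follow-up.** With event hazard λ and loss hazard m, the observed proportion is λ/(λ + m) × [1 − (1 − p)(1 − d)]. For true proportions of 20% and 40% this gives 18.6% and 35.2%, so a 20-point difference appears as 16.6 points. Simulated power is 75%, against 83% with equal 19% loss and 87% with full follow-up.

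**The case against.** The strongest reply is that ANOVA does little harm by itself. Steps 1 and 2 bear that out. A reader might infer that using ANOVA on counts and yes/no events biases the comparison; the calculations do not support that when chart follow-up is equal.

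A reader might also take the pilot as evidence that follow-up will be unequal. Section 2.1.2.6 says "Attrition among surviving participants was similar on the PRISM (25%) and usual care (14%) arms". That figure is at 6 months, excludes deaths and describes trial participation. Chart data at month 3 are abstracted by staff and do not depend on returned surveys. The plan itself assumes 72 evaluable in each arm. The 14% and 25% therefore serve only as a scenario. In that scenario the bias runs against PRISM, so it would not create false support for the hypothesis.

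It would be too strong to say that the plan makes no allowance for lost data: 11.5.3.6 names the relevant causes and cites a method for data truncated by death. What is missing is any link to these outcomes. Imputing a hospice referral after death has no clear meaning, and 14.2 does not say what censoring means for a chart count. Nor is ANOVA the only between-arm test of activation, because 11.5.2 also reaches the AYA Decision-Making Involvement scores. That overlap itself needs reconciling.

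Finally, total events by month 3 in all randomized AYAs is a legitimate quantity, and an offset is not neutral. If conversations cluster before death, short follow-up inflates the rate; one check built that way gave a ratio of about 1.06 under a true null. This stands, and it is why the offset model should not be reported alone.

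**Conclusion.** The point holds as a gap in a stated method for a secondary hypothesis. Section 11.5.3.2 prescribes group-only ANOVA for outcomes that are partly counts and yes/no events, and no section says how chart time shortened by death, transfer or loss enters the comparison.

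Its size depends on whether chart follow-up differs by arm. If it does not, the cost is about 1 to 4 points of power for counts and essentially nothing for yes/no events. If 14% against 25% were lost, a rate ratio of 1.5 would be reported as about 1.42, and power would be about 15 to 20 points lower than with a rate model. All event rates, dispersions, effects and loss patterns here are assumptions. The documents do not show that follow-up will differ by arm. The primary analysis and the sample size are unaffected.

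**What to change.** Reword 11.5.3.2 as follows:

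- **Decision-Making Involvement scores:** keep a linear model, adjusted for baseline score, age stratum and site, in line with 11.5.1 and 11.5.2. This also removes the conflict with group-only ANOVA.
- **Counts:** negative binomial regression, or Poisson with robust standard errors, in all randomized AYAs, with log chart follow-up time as offset and adjustment for age stratum and site. Add a sensitivity analysis of total events by month 3 without the offset, because events may cluster before death.
- **Yes/no events:** logistic regression with a reported adjusted risk difference, or cumulative incidence to month 3 with death as a competing event.
- **AYA participation:** the number of conversations with documented AYA participation, zero if none, so that the comparison does not depend on a conversation having occurred.
- **Follow-up rule:** define when chart follow-up starts and ends for death, transfer and loss, and say how the censoring in 14.2 applies to chart data.

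The cost is a few sentences and slightly more programming. Conversation dates are already abstracted; the end date of chart follow-up must also be recorded for each AYA. Effects for the chart outcomes would be reported as rate ratios or risk differences instead of mean differences.

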**1.2.3.4 Evaluate the impact of PRISM-AC on parent distress.**

**1.2.3.4.1 Outcome Measures:** parent anxiety (Generalized Anxiety Disorder Screener, GAD-7), depression (PHQ-8), and HRQOL (SF-36), 3-months post-enrollment.

**1.2.3.4.2 Hypothesis:** Parents of PRISM-AYAs will report lower anxiety and depression, and better HRQOL compared to parents of AYAs in usual care.

**1.2.3.4.3 Exploratory Outcome:** Family Experience (selected items from Hospital Consumer Assessment of Healthcare Providers and Systems [HCAHPS] survey).

**1.2.3.5** Evaluate the impact of PRISM-AC on family “palliative care activation.”

**1.2.3.5.1 Outcome measures:** (a) AYA- and parent- perceptions of AYA involvement in Decision-Making, measured with the Decision-Making Involvement Scale; (b) medical record documented goals of care conversations; and, (c) medical record documented AYA utilization of formal palliative care and other psychosocial services, hospice, limitation of intervention orders, and other advance care plans.

**1.2.3.5.2 Hypothesis:** PRISM families will demonstrate higher levels of activation compared to usual care.

**1.2.3.6** Explore longitudinal impact of PRISM-AC on above outcomes at 6-, 9-, and 12-months following enrollment.

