**9.6.1.1.5 Connor-Davidson Resilience Scale.** The Connor-Davidson Resilience Scale is a reliable and widely used instrument to measure inherent resiliency. Questions revolve around personal problem-solving and approaches to adversity. The 10-item instrument has high internal consistency (Cronbach’s alpha = 0.85), and has been used in diverse populations including adolescents, parents and cancer patients. Correlative studies have evaluated the scale with other psychosocial measures such as psychological distress, PTSD, and social support. It also has been used in pharmacologic and other intervention studies to model modifiable outcomes. Each item consists of a 5-point Likert scale (scored from zero to four) for total of 40 points. The mean score among well US adults is 31.8, with higher scores reflecting greater resilience. This instrument is included in the full (not abbreviated) surveys for both the run-in cohort and the RCT.

**9.6.1.1.6 Patient Activation Measure.** The 13-item PAM includes 3 domains to measure AYA or parent knowledge, confidence, and willingness to act regarding the AYA’s health. It is well-validated among chronically ill and healthy

adult populations, and studied among AYAs and parents of children with cancer. Both patient and parent versions have acceptable internal consistency and reliability ( $\alpha=0.86$  and 0.85, respectively). Items are scored on a 4 point Likert scale; responses are summed and transformed to 0-100. Higher scores suggest higher activation and thresholds distinguish 4 categories: (1) staying the course; (2) taking action; (3) confidence and knowledge to take action; and (4) believes active role important. This survey is only included in the run in.

**9.6.1.1.7 Benefit/Burden Scale for Children:** The Benefit/Burden Scale for Children (BBSC) was adapted by pediatric psychosocial clinicians from the Benefit Finding Scale for Children. BBSC measures benefit finding, illness-perceived burdens and psychological functioning in children. Factor analysis revealed a two-factor solution and each subscale had strong internal validity; benefit finding ( $\alpha = .852$ ; 10 items) and illness-related burden ( $\alpha = .804$ ; 10 items). All items are answered on a 5-point Likert scale ranging from “not at all” to “very much.” This survey is only included in the run in.

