**9.6.1.3 Both AYAs and Parents**

**9.6.1.3.1 The Decision-Making Involvement Scale (DMIS).** The 30-item DMIS was

developed to assess child and adolescent involvement in decisions having to do with illness management. Specifically, items assess child- and parent-behaviors that reflect the way children are involved in decisions, regardless of who ultimately makes the decision. Both AYAs and parents are asked to reflect on an important conversation from the past month and then respond to items based on a 4-point Likert Scale. Although there is a potential total score, instrument authors suggest scoring based on subscales assessing specific dimensions of involvement, including "child seek," "child express," "parent seek," "parent express," and "joint/options." Range of scores for each subscale = 0-4 and Cronbach's alpha = 0.68-0.71. This instrument is included in full and abbreviated surveys for the RCT.

**9.6.1.3.2 The Survey about Caring for Children with Cancer (SCCC).** This

questionnaire was developed from literature and focus groups of parents and medical providers to identify key domains relevant to caring for children with advanced cancer. Items were adapted from existing validated surveys and evidence-based guidelines. The survey has been extensively tested for content, wording, response burden, and cognitive validity. It has been used in multiple pediatric palliative care clinical trials, with several key analyses conducted by the PI. For this study, we included select items to assess parent-/patient- perceptions of prognosis, treatment goals, ability to express hopes and worries, as well as questions assessing satisfaction with overall care, and an ad-hoc checklist querying the number and duration of discussions the family has with health-care, psychosocial, or palliative care teams regarding prognosis, treatment goals, AYA hopes and worries, and to what degree AYAs

were involved in such discussions. This instrument is included in full and abbreviated surveys for the RCT and the run-in.

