### 11.3.1 Sample Size Determination and Power

**11.3.1.1** Our focus for sample size estimation is *the primary outcome: AYA PedsQL generic core scores at 3-month observation*. Sample size is based on published data from the pediatric advanced cancer population, where baseline scores were normally distributed with mean 70.9 and standard deviation 17.2. Assuming 26% attrition, we will randomize 195 AYAs (98 per arm) to obtain an evaluable sample size of 144 AYA participants (72 per arm). This sample size achieves 80% power to detect an 8.1 point difference in the mean 3-month total PedsQL score (Table 6).

**11.3.1.2** Power calculations for select secondary AYA outcomes are listed in Table 6.

**11.3.1.3** Parent Reported Outcomes: Assuming >90% caregiver participation (as in our prior studies), we anticipate a minimum sample size of 128 caregivers (64 per arm). This caregiver sample size achieves  $\geq 80\%$  power to detect reasonable effects for parent outcomes, based on standard deviations and other parameters from our preliminary data and published literature (Table 7).

**Table 7. Detectable Differences in selected Mean Instrument Scores Between Groups Given 80% Power and 5% Type I Error Rate**

Aim	Sample (N)	Outcome (Instrument)	Sample Mean (SD)	Source	MCID*	DD (SD)
1	AYAs (144)	Quality of Life – General (PedSQL 4.0)	70.9 (17.2)	Published Data 	4.4	8.1 (17.2)
		AYA Quality of Life – Cancer (PedSQL 3.0 Cancer)	65.3 (16.3)	Phase II RCT	(not published)	7.7 (16.3)
		Anxiety (HADS-A)	5.9 (3.4)	Phase II RCT	1.3-1.8	1.6 (3.4)
		Depression (HADS-D)	5.2 (3.6)	Phase II RCT	1.5	1.7 (3.6)
		AYA Hope (Hope Scale)	Mean 50 (8.3)	Phase II RCT	(not published)	3.9 (8.3)
2	Parents (128)	Anxiety (GAD-7)	2.95 (3.4)	Published Data 	(not published)	1.7 (3.4)
		Depression (PHQ-8)	3.3 (3.7)	Published Data 	5	1.8 (3.7)
		HRQOL-physical (SF-36 PCS)	50.3 (6.9)	Published Data 	3-5	3.4 (6.9)
		HRQOL-mental (SF-36 MCS)	42.9 (11.9)	Published Data 	3-5	5.9 (11.9)

Legend: MCID: Minimal Clinically Important Difference (\*reported when published); DD: Detectable Difference in Mean

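### The exploratory activation models reduce change to negative, null or positive with 'null' undefined, losing about a fifth to two fifths of the information in graded scores

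*Combined protocol and SAP*

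**What the plan says.** Section 11.5.3.2 sets out two steps for activation.

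- **Between-arm comparison.** "For all outcomes, results between trial groups will be compared using analysis of variance with trial group as the factor of interest". Nothing there says that scores are categorised first. This step addresses the hypothesis in Section 1.2.3.5: "PRISM families will demonstrate higher levels of activation compared to usual care".
- **Exploratory step.** "We will explore whether change in activation scores are correlated within families and/or modified by parent/child characteristics", "using ordinal logistic regression models with cumulative logits", "where change activation level is categorized as negative, null, or positive". The section gives no cut-points, no width for the null category and no reason for using three levels.

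The activation outcomes named in that section are AYA and parent DMIS scores, AYA participation in goals-of-care conversations, and chart-recorded service use. For the DMIS, Section 9.6.1.3.1 states: "Range of scores for each subscale = 0-4". Table 5 also lists the Survey about Caring for Children with Cancer (SCCC) under activation, and selected SCCC items are in the RCT surveys. The Patient Activation Measure, which has published thresholds for four levels, is not an RCT outcome. Section 9.6.1.1.6 says of it: "This survey is only included in the run in".

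**The concern.** No activation score named for the RCT comes with ready-made levels of change, so the rule turns a graded score into a direction. A very small gain on a DMIS subscale then counts the same as a large one.

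Because 'null' is undefined, the analyst must choose between an exact tie and a band of some width. That choice sets the category counts and affects the estimate. If it is left open, it can be made after the data are seen.

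The step also works on change without the baseline score as a covariate. Section 11.5.2 adjusts for baseline in the primary analysis, on the ground that change depends strongly on the starting value. On a 0 to 4 scale the same reasoning applies, since a participant near either end has little room to move further that way.

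What is at stake is the sensitivity of the modifier and within-family analyses, which are weak at this sample size in any case.

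**Working it through.** **Inputs from the documents.** Section 11.3.1 gives an "evaluable sample size of 144 AYA participants (72 per arm"), and 64 caregivers per arm. It gives no power, SD, effect size or baseline correlation for any activation outcome, so there is no activation figure to reproduce. The primary sample size does reproduce: 2 × (1.96 + 0.8416)² × (17.2/8.1)² = 70.8, or 71 per arm, and 195 × 0.74 = 144. It has no bearing on this point.

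**Assumptions.** The change score is normal with SD 1, and 'null' means within ±c SD. Neither is in the documents, so a range of c is shown.

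**1. Information kept by three levels.** For a shift in the mean, relative to the uncut score:

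ARE = Σ [φ(lower) − φ(upper)]² / p, summed over the categories, with limits measured from the mean change.

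- Mean change 0, no band: 2 × 0.3989² / 0.5 = 0.637.
- Mean change 0, c = 0.61: the middle category adds nothing by symmetry, so 2 × 0.3312² / 0.271 = 0.81. This is the best case.
- Mean change 0.5 SD, no band: 0.3521² / 0.309 + 0.3521² / 0.691 = 0.581.

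| Mean change (SD) | Null band (SD) | Information kept | Effective N of 144 | Power if 80% uncut |
|---|---|---|---|---|
| 0 | none | 64% | 92 | 61% |
| 0 | ±0.1 | 69% | 99 | 64% |
| 0 | ±0.3 | 76% | 110 | 69% |
| 0 | ±0.61 | 81% | 117 | 71% |
| 0.5 | none | 58% | 84 | 57% |
| 0.5 | ±0.61 | 77% | 111 | 69% |

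The last column is Φ(2.80 × √ARE − 1.96). A simulation of a two-group contrast (N = 144, shift 0.47 SD, 500 trials per setting) compared ordinary regression with a cumulative-logit model. Power was 80% against 63% at ±0.1, 82% against 72% at ±0.3, and 82% against 73% at ±0.61.

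**2. Further loss from not adjusting for baseline.** With score SD 1 and baseline correlation r, the change score has variance 2(1 − r) and the baseline-adjusted residual has variance 1 − r². Continuous change therefore keeps (1 + r)/2 of the information in the adjusted model: 75% at r = 0.5, 65% at r = 0.3, 85% at r = 0.7.

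**3. Power for the modifier test.** The plan gives no values, so assume 72 per arm, a balanced binary modifier (36 per cell), an interaction of 1.0 SD and r = 0.5. The change score then has SD 1 and the interaction has standard error √(4/36) = 0.333.

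- Continuous, baseline-adjusted: z = 3.0/√0.75 = 3.46; power Φ(1.50) = 93%.
- Continuous change: z = 3.0; power Φ(1.04) = 85%.
- Three levels, mean change 0: z = 3.0 × √ARE. At ±0.1 this is 2.48, power 70%. At ±0.61 it is 2.70, power 77%.

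Two simulations of this setting gave 92%, 82% and 70 to 74% in one, and 93%, 85% and 70 to 77% in the other, for bands of 0.1 to 0.61 SD. The differences are of the size expected from simulation error.

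The assumed interaction is large. At 0.5 SD every z halves, and power is about Φ(−0.23) = 41%, Φ(−0.46) = 32% and 24 to 27% respectively. The ordering is the same, but all three are weak.

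The loss in the within-family correlation was not computed.

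**The case against.** The strongest reply is that the step is declared exploratory, that direction-of-change coding is inefficient but not invalid, and that no confirmatory test uses it. All of that stands and sets the priority.

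Three stronger readings are tempting, and the documents do not support them.

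- **That the activation hypothesis is tested on collapsed scores.** It is not. The arms are compared by analysis of variance, and no categorisation is stated there.
- **That the trial loses some 20 to 30 points of power for its activation comparison.** A two-arm simulation (64 per arm, effect 0.5 SD, r = 0.5) gives 90% for a baseline-adjusted model against 60 to 71% for three levels. But that contrast is not what the plan analyses with this coding. About 10 of those points also come from ignoring baseline, since continuous change gives 80%.
- **That 'null' means an exact tie.** The plan does not say so. It leaves the term undefined, and a wider band loses less.

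Two limits of scope also stand. Chart items such as hospice referral or limits on resuscitation are counts or yes/no outcomes, so a continuous model does not suit them. And Section 11.5.2 extends the baseline-adjusted regression to secondary outcomes in the AYA surveys. That may cover the AYA DMIS in the arm comparison, but it does not reach the exploratory models, whose method Section 11.5.3.2 states separately.

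**Conclusion.** The point holds for the exploratory step only. For graded scores such as the DMIS subscales, the three-level coding keeps about 58 to 81% of the information in the change score. The exact share depends on a null band that the plan does not define and on the mean change. Omitting the baseline score costs a further part, a quarter at r = 0.5. For a modifier test under the stated assumptions, power is about 92 to 93% with a continuous baseline-adjusted model, 82 to 85% with continuous change and 70 to 77% with three levels.

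These figures rest on a normal change score, an assumed interaction of 1.0 SD and an assumed baseline correlation of 0.5. The documents give no DMIS parameters, so the figures show the size of the loss and do not predict this trial's power. Priority is low: the primary analysis, the between-arm activation test and every stated power figure are unchanged.

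**What to change.** In the exploratory part of Section 11.5.3.2:

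- model each week-12 DMIS subscale as continuous, with its baseline score as covariate and arm-by-modifier terms for the named characteristics;
- estimate AYA-parent correlation with a bivariate or mixed model;
- use count or logistic models for the chart-based outcomes;
- state how any SCCC items used as activation measures will be analysed;
- keep the negative/null/positive table as description only, with the null band fixed before the data are seen.

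The cost is a few sentences of SAP text. DMIS scores are already collected at baseline and week 12, so no new data, visits or participants are needed.
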